## 9.5. Vital Signs and Physical Examination

Descriptive summaries of actual values and changes from baseline will be calculated for supine systolic blood pressure, supine diastolic blood pressure, heart rate, respiratory rate, oral body temperature and weight by dose treatment group and visit/time point.

:

PCS criteria for vital signs are listed below

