Abbreviations: BAC-Symbol Coding = Symbol Coding from the Brief Assessment of Cognition; CAPS-5 = Clinician Administered PTSD Scale for DSM-5; [REDACTED] CGI-S = Clinical Global Impression – Severity; DES-II = Dissociative Experiences Scale-II; DNA = Deoxyribonucleic acid; ECG = electrocardiogram; HADS = Hospital Anxiety and Depression Scale; HIV = human immunodeficiency virus; LEC-5 = Life Events Checklist for DSM-5; [REDACTED] PCL-5 = PTSD Checklist for DSM-5; [REDACTED] PSQI = Pittsburgh Sleep Quality Index; PSQI-A = Pittsburgh Sleep Quality Index Addendum; PTSD = Post-Traumatic Stress Disorder; SCID-5-CT = Structured Clinical Interview for DSM-5 (Clinical Trials Version); [REDACTED]; S-STIS = Sheehan Suicidality Tracking Scale.

- a) Visit window is ± 3 days.
- b) Includes alcohol or illicit drug use history, employment status, smoking history, and index traumatic event.
- c) Collect vital signs after at least 5 minutes of rest, seated or supine.
- d) ECG after at least 5 minutes supine rest.
- e) Include body mass index calculation.
- f) Subjects use smartphone video application monitoring. Investigative site personnel calculate compliance and document accountability via capsule count/blister package inspection.
- g) Serious Adverse Event (SAE) reporting begins at time of informed consent and continues until 30 days after the last dose of study drug. Non-serious AE collection commences with the time of first dose of study drug until last day of subject participation in the study.
- h) Serum sample.
- i) Urine sample or breathalyzer (alcohol screen).
- j) Via phone.
- k) Doses are to be administered at the clinic on Day1 (after completing other procedures) then on an outpatient basis.

- l) Stage 2 dosing begins on the day after the Week 4 visit.
- m) Includes concurrent medical and psychiatric history.
- n) [REDACTED]
- o) Use interactive response technology for study drug dispensing.
- p) 7 days post-therapy.
- q) Clinical labs should be fasted except for screening.
- r) Only if required for adverse event follow-up.
- s) Rating based on the past month
- t) Rating based on the past week
- u) Use “since last visit” version after screening.
- v) Women of childbearing potential.
- w) Remote visit (optional. Only if necessary, due to COVID-19 health emergency)
- x) Visit window is  $\pm 7$  days.

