### **9.3. Stage 1: Day 1**

- Medical and psychiatric history updates (if applicable)
- Inclusion/exclusion criteria
- S-STS (since last visit version)
- Vital signs (after at least 5 minutes of rest, sitting or supine)
- Body weight
- ECG (after at least 5 minutes supine rest)
- Concomitant medications
- Laboratory tests
  - Clinical chemistry (fasted)
  - Hematology
  - [REDACTED]
  - [REDACTED]
  - Pregnancy test (urine) for women of childbearing potential
  - Drug (urine) and alcohol screen (breathalyzer)
  - Urinalysis
- Clinical measures (all measures except for CAPS-5 are not required if last measurement is within 14 days prior to Day 1)
  - CAPS-5
  - PCL-5
  - HADS
  - CGI-S
  - PSQI
  - PSQI-A

- [REDACTED]
- DES-II
- BAC-Symbol Coding
- Randomization
- Study drug dispensing, dose administration (in clinic and after completion of above-noted study procedures), and compliance monitoring
  - Medication adherence and reminder system training
- AEs (serious and non-serious)

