#### **9.4. Week 2, Day 14 ( $\pm 7$ days)**

- S-STS (since last visit version)
- Vital sign measurements (after at least 5 minutes of rest, sitting or supine)
- Body weight
- Laboratory tests: clinical chemistry (fasted)
- Clinical outcome measures
  - CAPS-5
  - PCL-5
  - HADS
  - PSQI
  - PSQI-A
  - CGI-S
- Study drug accountability, compliance review, and dispensing
  - Medication adherence and reminder system review
- Concomitant medications
- AEs (serious and non-serious)

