**Table 3 PCS criteria for vital signs**

Supine Systolic Blood Pressure	$\leq 90$ and decrease $\geq 20$ mm Hg; $\geq 180$ and increase $\geq 20$ mm Hg
Supine Diastolic Blood Pressure	$\leq 50$ and decrease $\geq 15$ mm Hg; $\geq 105$ and increase $\geq 15$ mm Hg
Supine Heart Rate	$\leq 50$ and decrease $\geq 15$ bpm; $\geq 120$ and increase $\geq 15$ bpm
Body Weight	Change(increase or decrease) from Baseline $\geq 7\%$
Respiratory Rate	$<12$ and $>20$ per minute

Frequency distributions of the vital signs of interest listed above will be summarized for PCS values at any post-baseline visit.

Physical Examinations will be listed.

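### SAP 9.5 and Table 3 restrict blood pressure summaries and the blood pressure and heart rate PCS flags to supine readings, although the protocol and the SAP's own schedule allow seated readings

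*SAP*

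**What the plan says.** **Collection.** Footnote c of protocol Table 4 reads: "Collect vital signs after at least 5 minutes of rest, seated or supine". The visit lists in protocol section 9 agree, for example Day 1, "Vital signs (after at least 5 minutes of rest, sitting or supine", and Week 2, "Vital sign measurements (after at least 5 minutes of rest, sitting or supine". Screening, Weeks 4, 6 and 8, early termination and the safety follow-up use equivalent wording. The footnotes to SAP Table 1 repeat the same permission. Where the protocol wants a supine reading it says so, as it does for the ECG.

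**Analysis.** SAP 9.5 states: "Descriptive summaries of actual values and changes from baseline will be calculated for supine systolic blood pressure, supine diastolic blood pressure". The sentence continues with "heart rate, respiratory rate, oral body temperature and weight by dose treatment group and visit/time point", where heart rate has no posture label. SAP Table 3 then sets PCS criteria for "Supine Systolic Blood Pressure", "Supine Diastolic Blood Pressure" and "Supine Heart Rate".

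**Related text.** Protocol 14.10.4 plans results and changes from baseline for each vital-sign measurement, without regard to position. SAP section 11, which lists departures from the protocol's analysis, does not mention a supine restriction. The data-handling conventions at the end of SAP 6.1.4 keep data that the plan does not analyze out of tables and graphs and put them in listings only.

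**The concern.** The analysis rule is narrower than the collection rule, and the SAP does not say what happens to a reading that meets the second but not the first. Changes in vital signs are part of the safety endpoint, so a programmer has to resolve this one way or the other.

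If *supine* is applied as a filter, valid seated readings leave the blood pressure summaries and the blood pressure and heart rate PCS counts. In active groups of about 26 subjects, that weakens what the tables can say about uncommon changes.

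If *supine* is treated as a loose label, all readings go in under a heading that may be untrue, and some changes from baseline may compare a seated value with a supine one. Within-subject switching is plausible: ECGs, which need supine rest, are scheduled at Day 1 and Weeks 4 and 8, while Weeks 2 and 6 have vital signs but no ECG. That is an inference from the schedule, not something the documents report.

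**Working it through.** The plan states no figure on this point, so there is none to reproduce. The check compares the texts and then sizes each reading under stated assumptions.

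**1. What a literal reading removes**

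| Item | Posture allowed at collection | Posture in the SAP analysis | Seated reading kept? |
|---|---|---|---|
| Systolic and diastolic summaries (9.5) | Seated or supine | Supine | No, listing only |
| Heart rate summary (9.5) | Seated or supine | None stated | Yes |
| Systolic, diastolic and heart rate PCS flags (Table 3) | Seated or supine | Supine | No, listing only |
| Respiratory rate, temperature and weight (9.5, and Table 3 where listed) | No relevant limit | None stated | Yes |

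**2. Size if seated readings are dropped**

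Inputs: 156 subjects randomized 4:1:1 (protocol 7.1). The seated share *s* is not in the documents, so a range is assumed, with each such subject seated at every visit.

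- Stage 1 groups: 156 × 4/6 = 104 placebo; 156 × 1/6 = 26 per dose.
- Stage 2, using the protocol's 15% Stage 1 dropout and 3:2:2 re-randomization: 104 × 0.85 × 2/7 ≈ 25 per dose, so the scale is similar.
- Subjects remaining per Stage 1 dose group = 26 × (1 − *s*).
- Upper one-sided 95% limit for the rate of an event not seen in *n* subjects = 1 − 0.05^(1/*n*).

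| Assumed *s* | Placebo left | Per dose left | Upper limit, no event seen in a dose group |
|---|---|---|---|
| 0% | 104 | 26 | 1 − 0.05^(1/26) = 10.9% |
| 25% | 78 | 19.5 (about 20) | 1 − 0.05^(1/20) = 13.9% |
| 50% | 52 | 13 | 1 − 0.05^(1/13) = 20.6% |
| 75% | 26 | 6.5 (6 to 7) | 39.3% (*n* = 6) to 34.8% (*n* = 7) |

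If position varied between visits, fewer subjects would be lost altogether, because the PCS count takes any post-baseline visit.

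**3. Size if the label is ignored and posture varies**

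Assume a posture shift of 5 to 10 mm Hg in a share *q* = 10% to 50% of subjects.

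- Added SD of change = shift × √(*q*(1 − *q*)): from 5 × √(0.1 × 0.9) = 1.5 to 10 × √(0.5 × 0.5) = 5 mm Hg.
- Expected drug-placebo bias when *q* is the same in each arm: 0. If *q* differed by 20 points between arms, it would be 0.2 × 5 = 1 to 0.2 × 10 = 2 mm Hg.
- Low-systolic flag (at most 90 mm Hg and a fall of at least 20), simulated with an assumed baseline mean of 120, baseline SD of 12 and change SD of 8 to 12: 0.2% to 1.7% of readings with no shift, 0.9% to 3.9% with a shift of −5, and 3.3% to 8.0% with a shift of −10. The last two ranges apply only to readings that carry the shift.

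Mixed posture can therefore add to flag counts, but in every arm.

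**The case against.** The strongest reply is that *supine* is a leftover label. If the database does not capture position, no filter can run and nothing is lost. If each subject keeps one position, changes from baseline are sound. Either may be true: the data collection forms and table shells are not available here, and the text of protocol 12.4.2, on vital sign measurement, is redacted and may contain a position instruction. That limits how far the consequence can be asserted. It does not remove the contradiction, which the SAP has with its own schedule as well as with the protocol.

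A reader might also infer more than the documents support:

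- *Seated subjects vanish from the safety tables.* They do not. Only the blood pressure summaries and the blood pressure and heart rate flags are affected, and the readings stay in listings.
- *Posture changes would be read as drug effects.* Allocation is randomized and blinded against placebo, so switching should be similar across arms and mainly adds noise.
- *Posture alone can trigger a flag.* Each blood pressure and heart rate criterion needs an absolute limit as well as a change. A subject at the screening ceiling of 95 bpm would have to rise by 25 to reach 120, and the 5 to 10 mm Hg shifts assumed above fall short of the 20 mm Hg systolic change. Posture may contribute to a flag; more than that is not shown.
- *Missing readings would follow site.* Nothing in the documents describes positioning practice by site.
- *The protocol has no rule on consistent position.* None is visible, but with 12.4.2 redacted, absence cannot be claimed.

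**Conclusion.** The point holds as a contradiction between the collection rule and the analysis rule for blood pressure, and for the heart rate PCS flag. As written, the SAP excludes readings that the protocol permits and plans to summarize, without declaring this as a change.

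The size is unknown because the seated share is unknown. Over the assumed 25% to 75% range, each Stage 1 dose group would keep roughly 20 down to 6 or 7 of 26 subjects in the affected tables. Those figures assume that the restriction is applied literally and that a seated subject is seated throughout. If the restriction is not applied, what remains is added noise and possible extra flags in all arms.

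This is a safety-reporting matter that should be settled before unblinding. It does not touch the primary analysis.

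**What to change.** First check whether the redacted protocol 12.4.2 gives a position instruction and whether position is captured in the database. Then amend the SAP only:

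1. In 9.5 and Table 3, delete *supine*, so that every protocol-permitted reading is summarized and screened against the PCS criteria.
2. Where position is recorded, compute change from a same-position baseline when one exists. State this in 9.5 as an exception to the last-observation baseline in 6.1.1.
3. Where no same-position baseline exists, still apply the PCS criteria, and mark the pair as mixed in the listing. Withholding the change component would make such readings impossible to flag and would bring back the loss of data.
4. If position is not recorded, say that readings are summarized regardless of posture.

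The cost is a few lines of SAP text and a little programming. The downside is some added noise from mixed positions. No protocol amendment is needed. One would require IRB review, and because the SAP is written against the amendment of 01 May 2020 with last enrolment estimated for June 2020, it would come late for most subjects.

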**Table 3 PCS criteria for vital signs**

Supine Systolic Blood Pressure	$\leq 90$ and decrease $\geq 20$ mm Hg; $\geq 180$ and increase $\geq 20$ mm Hg
Supine Diastolic Blood Pressure	$\leq 50$ and decrease $\geq 15$ mm Hg; $\geq 105$ and increase $\geq 15$ mm Hg
Supine Heart Rate	$\leq 50$ and decrease $\geq 15$ bpm; $\geq 120$ and increase $\geq 15$ bpm
Body Weight	Change(increase or decrease) from Baseline $\geq 7\%$
Respiratory Rate	$<12$ and $>20$ per minute

Frequency distributions of the vital signs of interest listed above will be summarized for PCS values at any post-baseline visit.

Physical Examinations will be listed.

## 9.6. Electrocardiograms

Descriptive summaries will be presented for ECG measures of PR interval, QRS interval, QT interval, QTc interval (both correction methods), and HR. These summaries will be presented by treatment group, Stage and visit.

The number and percentage of patients/subjects with normal and abnormal investigator reported ECG results will be summarized by visit and treatment group. An outlier analysis using QTcF will also be done based on these standard criteria. If the change from baseline QTcF values are > 30 or 60 msec, or if QTcF post baseline values are >450, 470 or 500. This will be done by Stage and Over All. Shift tables for results (normal, abnormal CS, abnormal NCS) from baseline to post-baseline visits will be presented by body system, treatment group, Stage and visit.

Bazett's correction (QTcb) and Fridericia's correction (QTcf) will be derived as follows:

Bazett's Correction (QTcb)	$QTc_b = \frac{QT_{msec}}{\sqrt{RR}}$
Fridericia's Correction (QTcf)	$QTc_f = \frac{QT_{msec}}{\sqrt[3]{RR}}$

Where: Relative Rate: RR = 60 / HR

HR = Heart Rate obtained from the ECG.

## 9.7. Concomitant Medication

The number and percentage of subjects using prior and concomitant medications will be grouped by ATC Level 4 and preferred name (coded based on Sept 2018 version of World Health Organization Drug Coding Dictionary [WHODD], and tabulated by stage and treatment group. In the case of multiple uses of the same medication within the same subject, each subject will only be counted once for each preferred name. Prior medications will be presented separately from concomitant medications. Medications that started prior to the first dose of study drug (Stage 1) will be considered prior medications whether or not they were stopped prior to the first dose of study drug. If a medication starts prior to the first dose and continues after the first dose of study drug, it will be considered both prior and concomitant. A medication will be determined as concomitant for each Stage if taken at any time during the reported timeframe.

Prior medications will be reported by Stage 1 treatment groups only. Concomitant medications will be reported for each Stage. If the use of concomitant medication starts in Stage 1 and ends after Stage 2 dose administration start date, it will be reported in Stage 1 and Stage 2 summary tables. Incidences will be displayed by treatment group. For

reporting in each Stage, subjects will be reported by the treatment received in their respective Stage.

## 10. Other Planned Analysis

## 10.2. COVID-19 Assessment Impact

To address the impact of COVID-19 on evaluating the efficacy of the trial, the following approach will be implemented:

- First describing the population : randomized date, visits missed, visits done remotely, restriction due to COVID-19 by visit. Restriction due to COVID-19 is defined as first day to stay at home, it will be defined by state.
- Second a sensitivity analysis on efficacy endpoints CAPS-5, PCL-5, PSQI score, HADS will be run. The main MMRM model will be run adding the COVID-19 restriction variable to evaluate impact of this covariate on treatment difference estimates. This covariate will be a time-varying covariate.
- A listing of all patient impacted by COVID-19 will be produced.

## 11. Changes from Protocol Planned Analysis

- Add mITT population for sensitivity analysis of primary efficacy.
- Add responder analysis for PCL-5.
- Add analysis for several subgroups
- Comparison of active treatment groups together is not relevant in this exploratory analysis without having any results on the comparison versus Placebo.
- Add COVID-19 Assessment Impact Analysis

### **13. Tables, Listings, and Figures**

All listings, tables and graphs will have a header showing the sponsor company name and protocol and a footer showing the version of SAS, the file name and path, and the source of the data (CRF page or listing number).

In general, one listing will be produced per CRF domain. All listings will be sorted by treatment, site, and subject number. All calculated variables will be included in the listings.

In all listings a blank line will be placed between each subject. Within a data listing, if an item appears line after line (e.g., repetition of subject number), then only the first occurrence will be displayed.

In data listings, the information for one subject will be kept on one page if at all possible, rather than splitting a subject's information across pages.

All tables, listings are described in the NYX-783-2004 SAP Shells latest document.

## 14. Appendix 1: PSQI Derivation

In order to calculate the PSQI total score first the following 7 variables need to be derived PSQIDURAT, PSQIDISTB, PSQILATEN, PSQIDAYDYS, PSQIHSE, PSQISLPQUAL, PSQIMEDS (noted as Q1A-Q1G in Section 6.1.4). All of them are added to give PSQI total score.

### **PSQIDURAT- DURATION OF SLEEP**

IF  $Q4 \geq 7$ , THEN set value to 0

IF  $Q4 < 7$  and  $\geq 6$ , THEN set value to 1

IF  $Q4 < 6$  and  $\geq 5$ , THEN set value to 2

IF  $Q4 < 5$ , THEN set value to 3

Minimum Score = 0 (better); Maximum Score = 3 (worse)

### **PSQIDISTB - SLEEP DISTURBANCE**

IF  $Q5b + Q5c + Q5d + Q5e + Q5f + Q5g + Q5h + Q5i + Q5j$  (IF Q5JCOM is null or Q5j is null, set the value of Q5j to 0) = 0, THEN set value to 0

IF  $Q5b + Q5c + Q5d + Q5e + Q5f + Q5g + Q5h + Q5i + Q5j$  (IF Q5JCOM is null or Q5j is null, set the value of Q5j to 0)  $\geq 1$  and  $\leq 9$ , THEN set value to 1

IF  $Q5b + Q5c + Q5d + Q5e + Q5f + Q5g + Q5h + Q5i + Q5j$  (IF Q5JCOM is null or Q5j is null, set the value of Q5j to 0)  $> 9$  and  $\leq 18$ , THEN set value to 2

IF  $Q5b + Q5c + Q5d + Q5e + Q5f + Q5g + Q5h + Q5i + Q5j$  (IF Q5JCOM is null or Q5j is null, set the value of Q5j to 0)  $> 18$ , THEN set value to 3

Minimum Score = 0 (better); Maximum Score = 3 (worse)

### **PSQILATEN - SLEEP LATENCY**

#### **First, recode Q2 into Q2new thusly:**

IF  $Q2 \geq 0$  and  $\leq 15$ , THEN set value of Q2new to 0

IF  $Q2 > 15$  and  $\leq 30$ , THEN set value of Q2new to 1

IF  $Q2 > 30$  and  $\leq 60$ , THEN set value of Q2new to 2

IF  $Q2 > 60$ , THEN set value of Q2new to 3

#### **Next**

IF  $Q5a + Q2new = 0$ , THEN set value to 0

IF  $Q5a + Q2new \geq 1$  and  $\leq 2$ , THEN set value to 1

IF  $Q5a + Q2new \geq 3$  and  $\leq 4$ , THEN set value to 2

IF  $Q5a + Q2new \geq 5$  and  $\leq 6$ , THEN set value to 3

Minimum Score = 0 (better); Maximum Score = 3 (worse)

### **PSQIDAYDYS- DAY DYSFUNCTION DUE TO SLEEPINESS**

IF  $Q8 + Q9 = 0$ , THEN set value to 0

IF  $Q8 + Q9 \geq 1$  and  $\leq 2$ , THEN set value to 1

IF  $Q8 + Q9 \geq 3$  and  $\leq 4$ , THEN set value to 2

IF  $Q8 + Q9 \geq 5$  and  $\leq 6$ , THEN set value to 3

Minimum Score = 0 (better); Maximum Score = 3 (worse)

### **PSQIHSE- SLEEP EFFICIENCY**

Diffsec = Difference in seconds between day and time of day Q1 and day Q3

Diffhour = Absolute value of diffsec / 3600

newtib = IF diffhour > 24, then newtib = diffhour - 24

IF diffhour  $\leq 24$ , THEN newtib = diffhour

(NOTE, THE ABOVE JUST CALCULATES THE HOURS BETWEEN GNT (Q1) AND GMT (Q3))

tmphse =  $(Q4 / \text{newtib}) * 100$

IF tmphse  $\geq 85$ , THEN set value to 0

IF tmphse  $< 85$  and  $\geq 75$ , THEN set value to 1

IF tmphse  $< 75$  and  $\geq 65$ , THEN set value to 2

IF tmphse  $< 65$ , THEN set value to 3

Minimum Score = 0 (better); Maximum Score = 3 (worse)

### **PSQISLPQUAL- OVERALL SLEEP QUALITY**

Q6

Minimum Score = 0 (better); Maximum Score = 3 (worse)

### **PSQIMEDS- NEED MEDS TO SLEEP**

Q7

Minimum Score = 0 (better); Maximum Score = 3 (worse)

### **PSQI TOTAL**

PSQIDURAT + PSQIDISTB + PSQILATEN + PSQIDAYDYS + PSQIHSE + PSQISLPQUAL + PSQIMEDS

Minimum Score = 0 (better); Maximum Score = 21 (worse)

Interpretation: TOTAL  $\leq 5$  associated with good sleep quality

TOTAL  $> 5$  associated with poor sleep quality
